6.2. Treatment Adherence

Participants in the Pfizer-BioNTech COVID-19 Vaccine and Moderna COVID-19 Vaccine treatment arms will receive two injections, while those in the placebo + Pfizer-BioNTech COVID-19 Vaccine and placebo + Moderna COVID-19 Vaccine treatment arms will receive three injections.

Treatment adherence will be summarized by treatment group within each cohort and overall. Study treatment administration data will be listed by treatment group, cohort (HA/MCD or Comparison) and participant.

7. ENDPOINT EVALUATION

7.1. Overview of Endpoint Analysis Methods

7.1.1. Multicenter Studies

Study participants will be recruited from 29 study sites. For the primary and secondary endpoints, study data will be analyzed as a whole, and no formal accommodation for site-to-site variation will be made.

7.1.2. Assessment Time Windows

Allowable visit windows for all scheduled visits are provided in Appendix 3 of the protocol. In the rare event a vaccination window cannot be met, vaccination may be scheduled beyond the +14-day window. If a participant becomes infected with SARS-CoV-2 or another acute illness following his/her first dose of vaccine, the second vaccination will be delivered, with allowance for a delay up to 90 days following the first dose.

Unscheduled visits may also occur throughout the study.

All data will be included in analyses, regardless of time of assessment. No formal accommodations will be made for out of window visits. Participants who are beyond the 14-day window will be summarized.

7.2. Primary Endpoints

The primary endpoints are as follows:

- The proportion of participants who experience a systemic allergic reaction (CoFAR Grade 2 and above regardless of tryptase, or CoFAR Grade 1 with elevated tryptase [1.2

x baseline plus 2 ng/ml]) within the 90-minute post-vaccination observation period to either dose of the Pfizer-BioNTech COVID-19 Vaccine.

- The proportion of participants who experience a systemic allergic reaction (CoFAR Grade 2 and above regardless of tryptase, or CoFAR Grade 1 with elevated tryptase [1.2 x baseline plus 2 ng/ml]) within the 90-minute post-vaccination observation period to either dose of the Moderna COVID-19 Vaccine.

7.2.1. Computation of the Primary Endpoints

The primary analyses will be conducted for participants enrolled under versions 1.0 through 4.0. For each population we will estimate the proportion of participants who experience a systemic allergic reaction (CoFAR Grade 2 and above regardless of tryptase, or CoFAR Grade 1 with elevated tryptase [1.2 x baseline plus 2 ng/ml]) within the 90-minute post-vaccination observation period to either dose of the Pfizer-BioNTech COVID-19 Vaccine and independently the Moderna COVID-19 Vaccine for both the HA/MCD and Comparison populations. These four proportions will be accompanied by their 95% exact (Clopper-Pearson) confidence intervals.

A systemic allergic reaction, categorized as yes or no, is defined as a participant having a reaction to either active dose 1 or active dose 2 (categorized as yes) or to neither active dose (categorized as no). Grade 1 systemic allergic reactions will only be categorized as yes if the tryptase is elevated as determined by the VCU lab. If the tryptase cannot be evaluated for a Grade 1 event (i.e. if missing a pre-treatment and/or post-treatment value), the study management team will determine the subjects categorization based on all available data for the subject.

Participants who do not have a systemic allergic reaction to the 1st active dose and missing data for their 2nd active dose will be removed from this analysis (complete case analysis).

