### **14. Statistical Considerations and Analytical Plan**

#### **14.1. Overview**

The primary research question of this study is to assess the proportion of participants who experience a systemic allergic reaction to either dose of the Pfizer-BioNTech COVID-19 Vaccine, and, independently, of Moderna COVID-19 Vaccine in HA/MCD and comparison populations. This objective will be addressed using a multi-center, randomized, initially-blinded (to the first injection), phase 2 trial in these two populations.

For adults, if no systemic allergic reactions are observed, the within vaccine sample size will be sufficient to rule out a rate as high as 1/275 in the HA/MCD population. If systemic allergic reactions are observed, the within vaccine sample size of 1700 participants was determined to detect a minimum proportion difference between these two populations of ~0.01 with at least 80% power. This translates to a true proportion of 1/100 vs. 1/10,000 in the HA/MCD and comparison populations, respectively.

For children, if no systemic allergic reactions are observed, the within vaccine sample size will be sufficient to rule out a rate as high as 1/50 in the HA/MCD population. If systemic allergic reactions are observed, the within vaccine sample size of 300 participants will detect a minimum proportion difference between the HA/MCD and comparison populations of ~0.05 with approximately 80% power. This translates to a true proportion of 1/20 vs. 1/10,000 in the HA/MCD and comparison populations, respectively.

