##### 14.4.2. Primary Analysis of Primary Endpoints

The primary analyses will estimate the proportion of participants who experience a systemic allergic reaction (CoFAR Grade 2 and above regardless of tryptase, or CoFAR Grade 1 with elevated tryptase [ $1.2 \times$  baseline plus 2 ng/ml]) within the 90-minute post-vaccination observation period to either dose of the Pfizer-BioNTech COVID-19 Vaccine and independently the Moderna COVID-19 Vaccine for both the HA/MCD and comparison populations. These four proportions will be accompanied by their 95% exact confidence intervals.

If systemic allergic reactions are observed, we will compare the proportions of participants experiencing a systemic allergic reaction to the Pfizer-BioNTech COVID-19 Vaccine and independently to the Moderna COVID-

19 Vaccine between the HA/MCD and comparison populations. The point estimate of the differences in proportions between populations within vaccines will be reported, together with their corresponding 95% exact unconditional confidence intervals. Exact p-values will be calculated using an unconditional test, as some cell counts are likely to have an expected value less than 5. No multiplicity adjustment will be applied for these two primary endpoints. Details of the implementation of the exact unconditional confidence intervals and p-value calculations will be included in the statistical analysis plan.

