**Table 14.7. Expected Rates, Number of Systemic Allergic Reactions, and Sample Size**

Rate (Number) Sample Size	Pfizer-BioNTech COVID-19 Vaccine	Moderna COVID-19 Vaccine	Total (Sample)
Comparison (40%)	0.0001 (0) 680	0.0001 (0) 680	1360
HA/MCD (60%)	0.01 (10) 1020	0.01 (10) 1020	2040
Total	0.006 (10) 1700	0.006 (10) 1700	0.006 (20) 3400

Under the scenario described in [Table 14.7](#), the proportion difference within a vaccine between the two populations is estimated at 0.01 with an unconditional exact 95% confidence interval (0.003, 0.018) and unconditional exact test p-value < 0.05. This illustration shows the expected precision of the estimated proportion difference under the assumed scenario.

This sample size also allows the following precision for estimation of risk in the HA/MCD group within each vaccine sample. If no reactions are observed out of 1020, the corresponding exact 95% confidence interval is (0, 0.0036), which rules out a risk as high as 1/275. If instead, the observed proportion is 10/1020 (i.e., about 0.01), then the 95% confidence interval is (0.005, 0.018).

For children, the within vaccine sample size of 300 participants was chosen. Under this scenario, we expect 180 in the HA/MCD population and 120 in the comparison population. This will detect a minimum proportion difference between

the two populations of approximately 0.05 with approximately 80% power, assuming a two-sided unconditional exact test. The proportion is assumed to be 0.0001 (1/10,000) in the comparison group and 0.05 (1/20) in the HA/MCD group.

Furthermore, a sample size goal of 300 children into the Pfizer-BioNTech COVID-19 vaccine allows for the following precision for the estimation of risk in the HA/MCD group. If no reactions are observed out of the 180 HA/MCD participants, the corresponding exact 95% confidence interval is (0, 0.020), which rules out a risk as high as 1/50. If instead the observed proportion is 2/180 (i.e., about 0.01), then the 95% confidence interval is (0.001, 0.039).

The sample size calculations do not account for dropouts since we expect that number to be extremely low. Although vaccine is widely available, there are difficulties getting into the registration systems and few individuals who receive an initial dose do not return for the second dose.

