7.2.2. Primary Analysis of the Primary Endpoint

If systemic allergic reactions are observed, we will compare the proportions of participants experiencing a systemic allergic reaction to the Pfizer-BioNTech COVID-19 Vaccine and independently to the Moderna COVID-19 Vaccine between the HA/MCD and comparison populations. The point estimate of the difference in proportions between populations within each vaccine is estimated as p_1-p_0 with $p_1=x_1/n_1$ and $p_0=x_0/n_0$ and will be reported, together with the corresponding 95% exact unconditional confidence interval. The proportion difference will be tested using a Barnard's Exact Unconditional Test with a two-sided test using the central method of doubling the one-sided p-value. No multiplicity adjustment will be applied to these two primary endpoints.

```
*** Primary Analysis (Barnard's);
ods output BarnardsTest=BarnardsTestOutput;
proc freq data = d_1 order = data;
  title "Primary";
  where dose = 'E' and protocol<5;
  tables group*resp / riskdiff;
  exact riskdiff barnard;
* High computational power, only run on an as needed basis;
run;
```

The p-value is equal to (BARNARDSTESTOUTPUT.NVALUE1)*2 where BARNARDSTESTOUTPUT.NAME1='XPL_RDIF1'.

```

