# R: Primary Analysis (Barnard's) p-value
library(exact2x2)
t <- with(d_1 %>% filter(dose == 'E' and protocol<5),
table(group,resp))
uncondExact2x2(t[1,2],sum(t[1,]),
t[2,2],sum(t[2,]),
alternative = "less",
parmtype = "difference",
method   = "score",
midp     = TRUE,
control  = ucControl(nPgrid=5000),
conf.int = FALSE)
```

Exact unconditional confidence limits for the risk difference are obtained with SAS procedure PROC FREQ and the RISKDIFF option in the EXACT statement. These RISKDIFF options request exact unconditional 95% confidence limits for the risk (proportion) and risk difference for the 2x2 table respectively. PROC FREQ computes the confidence limits by the tail method, which inverts two separate one-sided exact tests of the risk difference, where the tests are based on the score statistic (Chan and Zhang 1999). The size of each one-sided exact test is at most $\alpha/2$, and the confidence coefficient is at least $(1-\alpha/2)$.

If there is an issue with the calculation of the Barnard's Exact Unconditional Test, we will perform the Risk difference estimates, asymptotic 95% confidence intervals, and p-values using SAS procedure PROC FREQ and the RISKDIFF option without an EXACT statement.

```
*** Primary Analysis (Asymptotic);
proc freq data = d_1 order = data;
  title "Primary";
  where dose = 'E' and protocol<5;
  tables group*resp / riskdiff;
run;
```

Additionally, we will compare the proportion of participants experiencing a systemic allergic reaction (as defined in section 7.2.1) between HA/MCD adult (18 years and older at enrollment) and HA/MCD child (less than 18 years of age at enrollment) populations for each vaccine separately. Children who qualified for the study on the basis of uncontrolled allergic asthma will be excluded from this analysis. The point estimate of the difference in proportions between adult and child populations within each vaccine will be estimated along with its corresponding 95% exact unconditional confidence interval. The proportion difference will be tested using a Barnard's Exact Unconditional Test with a two-sided test using the central method of doubling the one-sided p-value. No multiplicity adjustment will be applied.

In the event that there are not enough subjects in a particular population, the reaction rate will be described descriptively.

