7.2.3. Sensitivity Analyses of the Primary Endpoint

Missingness (not due to allergic reaction) will be evaluated for each vaccine type separately in each age group. If more than 5% of participants are missing their second active dose for either the Pfizer-BioNTech COVID-19 Vaccine or the Moderna COVID-19 Vaccine, a sensitivity analysis using the tipping-point approach will be conducted to assess the robustness of the primary analysis results. This analysis will only be conducted in the vaccine arm(s) with more than 5% missing. Participants missing both active doses will not be imputed. Tipping point analysis explores the influence of missingness on the overall conclusion from statistical inference by positing a wide spectrum of assumptions regarding the missingness mechanism (from less conservative to more conservative). The analysis finds a (tipping) point in this spectrum of assumptions, at which conclusions of the analysis change. After such a tipping point is determined, clinical judgment can be applied as to the plausibility of the assumptions underlying this tipping point.

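### SAP 7.2 restricts the primary HA/MCD-versus-comparison analysis to versions 1.0–4.0 and Section 11 does not record it, so the child contrast sized in the protocol has no specified primary-endpoint analysis for children enrolled under versions 5.0–8.0

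*SAP*

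**What the plan says.** Protocol 14.4.2 describes the primary analysis for both populations and each vaccine, with exact intervals. If reactions occur, it adds a between-population comparison: "The point estimate of the differences in proportions between populations within vaccines will be reported". It gives no restriction by version or age.

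Protocol 14.1 sizes adults and children separately. For children, "the within vaccine sample size of 300 participants will detect a minimum proportion difference between the HA/MCD and comparison populations of ~0.05", with power of about 80%. Protocol 14.7 gives the split: "Under this scenario, we expect 180 in the HA/MCD population and 120 in the comparison population". The assumed rates are 0.05 and 0.0001, with a two-sided unconditional exact test.

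SAP 7.2.1 then narrows the scope: "The primary analyses will be conducted for participants enrolled under versions 1.0 through 4.0". All three code blocks in SAP 7.2.2 carry this out. The SAS Barnard and asymptotic blocks use "where dose = 'E' and protocol<5", and the R block uses "filter(dose == 'E' and protocol<5".

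Under the protocol's inclusion criteria, versions 1.0–4.0 took ages 12 and over, and versions 5.0–8.0 take ages 5 to 17 only. SAP Section 11, which lists changes from the protocol's analyses, has one entry, on the as-treated sample.

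SAP 7.2.2 does plan one test on the primary endpoint that uses children, "between HA/MCD adult (18 years and older at enrollment) and HA/MCD child (less than 18 years of age at enrollment) populations". SAP 7.2.3 adds: "Missingness (not due to allergic reaction) will be evaluated for each vaccine type separately in each age group".

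**The concern.** A stated power presupposes a test. The protocol gives a power for HA/MCD against comparison children, and the SAP's version cut-off removes from that test everyone enrolled in the child-only phase. The adult-versus-child test does not replace it, because it lies within HA/MCD and leaves out the comparison children.

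Two things are at stake. First, if the SAP is followed as written, a contrast with published power goes unperformed on the primary endpoint, and any later version of it would be post hoc. Second, someone checking Section 11 for departures from the protocol would not learn that the scope of the primary analysis had been cut.

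**Working it through.** **1. Reproduce the child power.** Inputs from protocol 14.7: n = 180 and 120, rates 0.05 and 0.0001, two-sided unconditional exact test. Alpha of 0.05 is stated for the 1,700-participant calculation and is assumed to apply to children too. From SAP 7.2.2: Barnard's test, with the one-sided p-value doubled. The statistic is the pooled score, T = (x1/n1 − x0/n0) / √[p(1−p)(1/n1 + 1/n0)] with p = (x1+x0)/(n1+n0). The one-sided p-value is the maximum of P(T ≥ observed) over the common rate.

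| Reactions, HA/MCD v comparison | Doubled p |
|---|---|
| 6 v 0 | 0.0546 |
| 7 v 0 | 0.0373 |
| 9 v 1 | 0.0607 |
| 10 v 1 | 0.0495 |

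Rejection therefore starts at 7 v 0, or at 10 v 1. Power at the planned rates:

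- No comparison reactions: P(X ≥ 7 | 180, 0.05) × 0.9999^120 = 0.7907.
- One comparison reaction: P(X ≥ 10 | 180, 0.05) × 120 × 0.0001 × 0.9999^119 = 0.4126 × 0.01186 = 0.0049.
- Sum: 0.7956, or 79.6%.

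This agrees with the stated figure of about 80%. Mid-p doubling gives the same value and Fisher's test 79.4%. A two-sided ordering on |T| gives 88.5%, but SAP 7.2.2 specifies doubling.

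**2. What the test could show at lower rates** (same method, comparison rate 0.0001):

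| HA/MCD rate | Power |
|---|---|
| 0.05 | 79.6% |
| 0.04 | 57.8% |
| 0.03 | 29.4% |
| 0.02 | 7.0% |
| 0.01 | 0.2% |

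For comparison children, 0 reactions in 120 would give an exact upper limit of 1 − 0.025^(1/120) = 0.0303, about 1/33. The SAP specifies no such interval on the primary endpoint for those enrolled under versions 5.0–8.0.

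**3. Who is left out.** Versions 1.0–4.0 had a minimum age of 12, so no child aged 5 to 11 can satisfy the code filter. Children aged 12 to 17 satisfy it only if enrolled early. The documents give no count of these, and protocol 4.1 describes enrolment to that point as very largely adult. If all 300 planned children come in under versions 5.0–8.0, none enters the HA/MCD-versus-comparison test.

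**4. Whether another planned analysis covers it.**

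| Place | What it gives | What is missing |
|---|---|---|
| SAP 7.2.2, adult v child | Primary endpoint, defined by age with no version filter | HA/MCD only; asthma-qualified children excluded |
| Protocol 14.4.4 | Pooled adult-and-child analysis | Exploratory; only if HA/MCD rates are similar; not child-specific; no SAP code |
| SAP 7.3.1, 7.3.2 | Grade 3 or higher; Brighton Levels 1–3; analysed as in 7.2.2 | Different, more severe endpoints |
| SAP 7.3.5 | Grade 2 or higher within 48 hours; analysed as in 7.2.2 | Omits Grade 1 with raised tryptase; adds reactions after 90 minutes |
| SAP 7.2.4 | Per-dose rates by vaccine, no version limit | Not split by population; no interval specified |
| SAP 7.2.2, closing fallback | Descriptive rate if a population is too small | No interval or contrast specified |
| SAP 8.1–8.2 | Safety displays by age group and cohort | Adverse-event categories, no endpoint interval; the Fisher test compares study arms |

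SAP 7.3 adds its own ambiguity. It limits secondary endpoints to versions 1.0–4.0, then allows adults to be analysed apart from children if enough children are enrolled. Since those versions already admitted 12-year-olds, it is unclear whether children enrolled later are meant.

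**The case against.** The strongest reply is that the missing test is inferred. No objective names a child-only HA/MCD-versus-comparison test. The child objectives concern adults against children within HA/MCD, protocol 14.4.3 specifies only that contrast for children, and SAP 7.2.2 carries it out. Protocol 4.1 says children were added to learn whether age is a risk factor. On this view, 14.1 and 14.7 merely say what 300 children could detect. This stands as a limit on the point: the intent comes from the sizing text alone. It does not remove the mismatch, because a power for a two-sided exact test with no matching analysis needs either the analysis or a correction.

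A separate primary set is also defensible. Versions 5.0–8.0 differ in allocation, vaccine blinding, placebo interval and blood sampling, and the protocol sizes adults and children apart. That supports keeping the cut-off. It does not explain why Section 11 omits it.

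Third, little inferential information is lost: power is 7.0% at an HA/MCD rate of 2% and 0.2% at 1%, and comparison-child reactions would still appear in the safety displays. This stands, and is why the added analysis should be labelled supportive. The exact intervals would be informative whatever the test shows.

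A reader might go further and infer that children under versions 5.0–8.0 have no primary-endpoint analysis at all. The documents do not support that: HA/MCD children under 18 enter the adult-versus-child test, where no version filter is stated.

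**Conclusion.** The point holds as a mismatch between the protocol's sizing text and the SAP, together with an unrecorded restriction of the primary analysis. It should be fixed. For children enrolled under versions 5.0–8.0, the SAP specifies no HA/MCD-versus-comparison analysis on the primary endpoint, although the protocol gives that contrast about 80% power at 180 against 120. Other planned analyses cover it only in part.

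The finding about text rests on 14.4.2 having no version limit and on the cut-off appearing in both SAP text and code. The 79.6% rests on alpha 0.05, the doubled p-value, the full 180 and 120, and the assumed rates of 0.05 and 0.0001.

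Two stronger conclusions do not follow. The child power figure is not wrong, since it reproduces. Nor is the primary test in versions 1.0–4.0 weakened, because the restriction leaves its participants and method as they are.

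**What to change.** 1. Choose one of two routes.
   - Add to SAP 7.2 a supportive HA/MCD-versus-comparison analysis in children, by vaccine, using the age definition already in 7.2.2 (under 18 at enrolment). Report Clopper-Pearson proportions, the risk difference with its exact unconditional interval, and Barnard's test. Note that 12- to 17-year-olds from versions 1.0–4.0 also sit in the primary set, so the two analyses overlap. State whether asthma-qualified children are included, since protocol 14.4.3 excludes them only from adult versus child.
   - Or state that the child contrast is descriptive (proportions with exact intervals by population) and remove the child power statements from protocol 14.1 and 14.7.
2. State that children in SAP 7.2.2 (adult versus child) and in 7.3 include those enrolled under versions 5.0–8.0.
3. List the version restriction in SAP Section 11.

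The first route costs some SAP wording and one more run of existing code with an age filter in place of the version filter. It adds one unadjusted supportive test per vaccine with child data, which at 180 against 120 rejects only from 7 v 0. The second route costs wording in both documents. Neither needs new participants or data.

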#### 14.3. Measures to Minimize Bias

To minimize bias, a randomization schedule will be generated by the SACCC and implemented in a validated system that will be used by site personnel to automate the random assignment. For protocol versions 1.0 - 4.0, participants were randomized 2:2:1:1 to receive either the Pfizer-BioNTech COVID-19 Vaccine, Moderna COVID-19 Vaccine, placebo + Pfizer-BioNTech COVID-19 Vaccine, or placebo + Moderna COVID-19 Vaccine. For protocol versions 5.0 – 8.0, participants will be randomized 2:1 to receive active vaccine alone or placebo + active vaccine. The Pfizer-BioNTech COVID-19 Vaccine will be the active vaccine distributed initially.

The randomization scheme will be reviewed and approved by a statistician at the SACCC and will not be modified thereafter except to accommodate any changes required by amendments to the protocol. Furthermore, all first doses of active and placebo vaccine will be blinded to the participant, and all site staff except the unblinded pharmacist and any unblinded personnel administering vaccine and/or scheduling visits. All laboratory assays will be performed by laboratory technicians who do not know the participants' group assignments.

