#### 14.7. Sample Size Considerations

The within vaccine sample size of 1700 participants, 1020 in the HA/MCD population and 680 in the comparison population was determined to detect a minimum proportion difference between the two populations of approximately 0.01 with at least 80% power, assuming a two-sided unconditional exact test. The proportion is assumed to be 0.0001 (1/10,000) in the comparison group and 0.01 (1/100) in the HA/MCD group (see [Table 14.7](#)). Power was calculated using an unconditional exact test, with the significance level of the test targeted at 0.05.

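### SAP 7.2.1 leaves Grade 1 reactions without evaluable tryptase to case-by-case classification, with no stated masking to allergy population and no analysis under the alternative classification

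*SAP*

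**What the plan says.** SAP 7.2.1 counts a Grade 1 reaction as an event only when a named laboratory finds tryptase elevated. The exception reads "If the tryptase cannot be evaluated for a Grade 1 event (i.e. if missing a pre-treatment and/or post-treatment value"; in that case "the study management team will determine the subjects categorization based on all available data for the subject". It gives no criteria, no masking, no timing relative to the primary tables and no default category.

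The classification feeds the primary contrast of HA/MCD against comparison participants. SAP 7.2.2 says "The point estimate of the difference in proportions between populations within each vaccine is estimated as p_1-p_0", tested with Barnard's test as a "two-sided test using the central method of doubling the one-sided p-value".

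The masking text covers other people and other assignments:
- Protocol 3.5.2 keeps clinical assessors unaware of placebo or vaccine, and of which vaccine, at the first visit. It does not mention population.
- Protocol 14.3 covers the laboratory: "All laboratory assays will be performed by laboratory technicians who do not know" the group assignments.
- Protocol 3.6 provides for unblinding a participant who reacts to the first injection, after the day 4 diary review.

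The only sensitivity analysis of the primary endpoint, SAP 7.2.3, is triggered when more than 5% of participants lack a second active dose.

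**The concern.** Taken at face value, all of a participant's data includes whether that person is in the HA/MCD or the comparison group. The rule therefore allows the outcome to be assigned with knowledge of the exposure under comparison. If allergy history influenced the call, the difference between populations would be biased directly, and no planned table of the primary endpoint would show how far the result rests on these calls. Laboratory masking does not help, because the rule applies only when the laboratory value is missing.

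The stakes come from the small number of events. The protocol's sample-size table expects about 10 events against 0 within each vaccine, so one participant carries much of the weight. The reach is wider than the primary test: the adult v child comparison in SAP 7.2.2 and secondary endpoints 3 to 5 use the same reaction definition.

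**Working it through.** **Inputs.** Protocol 14.7 gives "1020 in the HA/MCD population and 680 in the comparison population" within each vaccine, assumed proportions of 0.01 and 0.0001, and a test "with the significance level of the test targeted at 0.05". SAP 7.2.2 gives the test and the doubling.

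**Method.** For x1 events among n1 = 1020 HA/MCD participants and x0 among n0 = 680 comparison participants, the pooled score statistic is

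z = (x1/n1 − x0/n0) / √[p̄(1 − p̄)(1/n1 + 1/n0)], with p̄ = (x1 + x0)/(n1 + n0).

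The one-sided p-value is the probability of a statistic at least this large, maximised over the common proportion from 0 to 1, and then doubled. The mid-p variant in the SAP's R code puts the 0.05 cut-offs in the same places.

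**The plan's own figures first.**
- Expected events are 1020 × 0.01 = 10.2 and 680 × 0.0001 = 0.068, shown in the protocol table as 10 and 0.
- The test rejects for x1 ≥ 7 when x0 = 0, x1 ≥ 11 when x0 = 1, and x1 ≥ 14 when x0 = 2. Summing the binomial probabilities over that region gives power of 85.4%, consistent with "approximately 0.01 with at least 80% power".
- Clopper–Pearson limits are 0 to 0.0036 for 0/1020, and 0.0047 to 0.0180 for 10/1020. Both match the protocol.
- At 10 v 0, p = 0.012, matching the protocol's statement that p is below 0.05.

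**Effect of one reclassification.**

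| HA/MCD v comparison | Doubled Barnard p |
|---|---|
| 6 v 0 | 0.056 |
| 7 v 0 | 0.038 |
| 7 v 1 | 0.137 |
| 10 v 0 | 0.012 |
| 10 v 1 | 0.051 |

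One HA/MCD call separates 6 v 0 from 7 v 0. One comparison-group call turns 7 v 0 into 7 v 1, or the planned 10 v 0 into 10 v 1.

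**Effect on the estimate.** One HA/MCD event is worth 1/1020 = 0.0010 and one comparison event 1/680 = 0.0015. At 10 v 0 the difference is 10/1020 = 0.0098; at 10 v 1 it is 0.0098 − 0.0015 = 0.0083, about 15% smaller.

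**How firm the cut-offs are.** For these tables the maximum falls at a common proportion close to 1. If the search were confined to proportions below 0.5, 6 v 0 would give 0.045 and 10 v 1 would give 0.036. The boundary would then lie between 5 v 0 (0.068) and 6 v 0, and 7 v 1 would give 0.124. The exact cut-off depends on that range; the sensitivity to one event does not. Fisher's exact test has the same 6/7 boundary (0.087 and 0.046).

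**The case against.** **The SAP does not say that the team is unmasked.** A reader might infer that it calls for unmasked review, or that population will be used in the decision. It says neither; it is silent. This stands, and the point is limited to the absence of any provision withholding population or vaccine.

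**The rule should seldom be used.** The primary analysis is restricted to versions 1.0–4.0. Protocol 10.1 has tryptase drawn there at every visit before vaccination and at 1 hour and/or 30–60 minutes after onset, with further samples for later reactions and at discharge. Protocol section 10 has it analysed in real time for reactors. The sparser schedule for versions 5.0–8.0 falls outside this set. This also stands.

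**The p-values show rare-event fragility in general.** Any single event would move them, and from 10 v 0 it takes four HA/MCD events reclassified as non-events to lose significance (7 v 0 is still 0.038). Losing it through 10 v 1 requires a comparison-group case to be called yes, which runs against the bias one would expect. This is correct, but the expected bias also works by calling such a case no. That leaves p at 0.012 where the other classification gives 0.051.

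**Estimation comes first.** Protocol 1.1 treats the HA/MCD proportion and its interval as a key finding whatever the rate, and the test is conditional on reactions occurring. This is a reason to show bounds for the proportions and intervals as well as the p-value.

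**Other analyses give some view.** Secondary endpoint 6 (Grade 2 and above, no tryptase component) excludes all Grade 1 events and is analysed as in SAP 7.2.2. But it uses a 48-hour window and also drops Grade 1 events with confirmed tryptase elevation, so it does not isolate this rule.

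**CoFAR grading remains with the site investigator**, who knows the population. This stands as a limit on what masking this one step can achieve.

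**Conclusion.** The point holds in a limited form. The SAP adopts a discretionary rule for part of the primary endpoint, does not withhold the compared exposure from those applying it, and plans no primary-endpoint analysis under the other classification. At the planned size, one such call can move the result across 0.05 in either direction.

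The documents do not support a claim that classification will be unmasked, that it will be biased, or that many events will be affected. No count of unevaluable Grade 1 reactions is given, so the size is conditional: nil if there are none, and potentially decisive for the test with one if the count is near a boundary. The p-values assume the full 1020 v 680; actual enrolment under versions 1.0–4.0 is not stated. They also assume maximisation over the whole range of the common proportion. This is a cheap improvement, not a flaw that undermines the design.

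**What to change.** Add two provisions to SAP 7.2.1:

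1. Classify Grade 1 reactions with unevaluable tryptase from the reaction record, with population, vaccine and arm removed, before the primary tables are run.
2. Report the number of such reactions by population and vaccine. Repeat the primary proportions, confidence intervals and test with all of them counted as yes, and again with all counted as no.

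The cost is one masked listing for the existing team and two extra rows in the primary table. If no such reactions occur, neither is needed. The change does not mask the site investigator's CoFAR grading, and the SAP should not suggest that it does.
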